9.4 Analysis Plan

9.4.1 Primary endpoint analysis:

The primary study objective is to assess the overall response rate (ORR) of ramucirumab plus pembrolizumab. To do so, we will use Simon's two-stage design.²⁰ This design is implemented by first enrolling a small group of patients and then enrolling a second group of patients in the second stage conditional on an adequate number of responses in the first group. Response rate with single agent IO is around 10% and we would consider a response rate of at least 25% to be interesting for further study. The optimal two-stage design to test the null hypothesis that $P \leq 0.10$ versus the alternative that $P \geq 0.25$ will include 13 patients in the first stage. After testing the drug on 13 patients in the first stage, the trial will be terminated if 1 or fewer respond. If the trial goes on to the second stage, an additional 21 patients will be included for a total of 34 patients studied. If the

total number responding is less than or equal to 5, the drug is rejected. This design has an expected sample size of 20.95 and a probability of early termination of 0.621. The sample size was calculated using PASS 16 and assuming $\alpha = 0.10$ with a desired power of 80%.

Overall survival and progression-free survival as continuous time-to-event outcomes: All evaluable patients will be used for this analysis. Kaplan-Meier curves will be used to estimate overall survival, measured from the date of study registration to the date of event (i.e., death) or the date of last follow-up if no event has occurred at their last evaluation. We will further consider Cox proportional hazards models to explore a limited set of confounding factors.

9.4.2 Analysis of secondary endpoints:

Secondary objectives involve evaluating safety and tolerability and estimating PFS and overall survival. Descriptive statistics will be calculated for these outcomes and Kaplan-Meier curves will be calculated to estimate PFS and OS. Patients who have reached the end of the study but not progressed will be considered censored at the last documented date of contact. Estimates from this analysis will be used as preliminary data to inform future research.

Overall response. All evaluable patients (i.e. eligible patients who have received at least one dose of the treatment) will be assessed in terms of their best response to therapy. Those who achieve a partial response (PR) or complete response (CR) will be considered responses and the overall response rate will be calculated as the number of PRs and CRs divided by the total number of evaluable patients. We will also perform analysis of disease control rate (CR + PR + SD). These estimates will be accompanied by exact binomial confidence intervals as well.

Safety and Tolerability. Frequency and severity of adverse events and tolerability of the regimen will be collected and summarized by descriptive statistics for each of the disease cohorts. As per NCI CTCAE v 5.0, the term toxicity is defined as adverse events that are classified as either possibly, probably, or definitely related to study treatments. The maximum grade for each type of toxicity will be recorded for each patient, and frequency tables will be reviewed to determine toxicity patterns. In addition, we will review all adverse event data that is graded as 3, 4, or 5 and classified as either “unrelated” or “unlikely to be related” to study treatment in the event of an actual relationship developing. The incidence of severe (grade 3+) adverse events or toxicities will be described. We will also assess tolerability of the regimens through assessing the number of patients who required dose modifications and/or dose delays. In addition, we will also capture the proportion of patients who go off treatment due to adverse reactions or even those who refuse further treatment for lesser toxicities that inhibit their willingness to continue participation on the trial. All patients who have received at least one dose of the therapeutic agent in this study will be evaluable for toxicity and tolerability. This is detailed in Table 7.

Table 7: Evaluating Adverse Events

V5.0 CTCAE Grading	Grade 1	Mild; asymptomatic or mild symptoms; clinical or diagnostic observations only; intervention not indicated.
	Grade 2	Moderate; minimal, local or noninvasive intervention indicated; limiting age-appropriate instrumental ADL.
	Grade 3	Severe or medically significant but not immediately life-threatening; hospitalization or prolongation or hospitalization indicated; disabling; limiting self-care ADL.
	Grade 4	Life threatening consequences; urgent intervention indicated.
	Grade 5	Death related to AE
Seriousness	
A serious adverse event is any adverse event occurring at any dose or during any use of investigational product that:
 
†Results in death; or
 
†Is life threatening; or places the participant, in the view of the investigator, at immediate risk of death from the event as it occurred (Note: This does not include an adverse event that, had it occurred in a more severe form, might have caused death.); or
 
†Results in a persistent or significant disability/incapacity (substantial disruption of one's ability to conduct normal life functions); or
 
†Results in or prolongs an existing inpatient hospitalization (hospitalization is defined as an inpatient admission, regardless of length of stay, even if the hospitalization is a precautionary measure for continued observation. (Note: Hospitalization for an elective procedure to treat a pre-existing condition that has not worsened is not a serious adverse event. A pre-existing condition is a clinical condition that is diagnosed prior to the use of the investigational products and is documented in the patient's medical history.); or
 
†Is a congenital anomaly/birth defect (in offspring of participant taking the product regardless of time to diagnosis); or
 
Is a new cancer (that is not a condition of the study) (although not serious per ICH definition, is reportable to the Sponsor within 24 hours, to Merck within 2 working days and to Lilly within 15 days to meet certain local requirements); or
 
Is an overdose (whether accidental or intentional). Any adverse event associated with an overdose is considered a serious adverse event for collection purposes. An overdose that is not associated with an adverse event is considered a non-serious event of clinical interest and must be reported within 24 hours to the Sponsor and to Merck within 2 working days and to Lilly within 15 days.
 
Other important medical events that may not result in death, not be life threatening, or not require hospitalization may be considered a serious adverse event when, based upon
	

	appropriate medical judgment, the event may jeopardize the participant and may require medical or surgical intervention to prevent one of the outcomes listed previously (designated above by a †).
Duration	Record the start and stop dates of the adverse event. If less than 1 day, indicate the appropriate length of time and units
Action taken	Did the adverse event cause investigational agent to be discontinued?
Relationship to Investigational Product	Did investigational agent cause the adverse event? The determination of the likelihood that investigational agent caused the adverse event will be provided by an investigator who is a qualified physician. The investigator's signed/dated initials on the source document or worksheet that supports the causality noted on the AE form, ensures that a medically qualified assessment of causality was done. This initialed document must be retained for the required regulatory time frame. The criteria below are intended as reference guidelines to assist the investigator in assessing the likelihood of a relationship between the test drug and the adverse event based upon the available information. The following components are to be used to assess the relationship between investigational agent and the AE; the greater the correlation with the components and their respective elements (in number and/or intensity), the more likely investigational agent caused the adverse event (AE):
Exposure	Is there evidence that the participant was actually exposed to investigational agent such as: reliable history, acceptable compliance assessment (pill count, diary, etc.), expected pharmacologic effect, or measurement of drug/metabolite in bodily specimen?
Time Course	Did the AE follow in a reasonable temporal sequence from administration of investigational agent? Is the time of onset of the AE compatible with a drug-induced effect (applies to trials with investigational medicinal product)?
Likely Cause	Is the AE not reasonably explained by another etiology such as underlying disease, other drug(s)/vaccine(s), or other host or environmental factors

9.5 Analysis of Exploratory Endpoints - Correlative studies:

Several correlative markers will be explored in this trial in relation to clinical outcomes of interest, and in particular in relation to the primary endpoint of response rate. Statistical analysis corresponding to the correlative studies will be descriptive and exploratory in nature.

For immune cell subpopulation data by flow cytometry, we will identify differences between the paired PBMC samples from the same patients. TCR immunoSEQ data will be summarized for each patient for T-cell clonality difference, descriptive statistics and confidence interval will be obtained across patients.

To study the association of immune cell subpopulations among blood and the tumor microenvironment, we will use linear mixed-effects models for repeated measurements within patients. A bivariate plot will be used to describe the relationship between response rate and peak VEGF via ELISA over time. Results will be summarized using descriptive statistics (i.e. means, medians, standard deviations, 95% confidence intervals for continuous variables, and frequencies for discrete data). The limited sample will not provide sufficient power for formal hypothesis testing (except to detect very large differences in these markers), but the preliminary data will be used to explore potential relationships and differences using graphical analyses and quantitative summaries of these markers. These results and exploratory analyses will also be used in planning a future randomized study of this combination treatment regimen in this patient population.

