 - Completion of 35 treatments (approximately 2 years) with pembrolizumab
- Patients who complete 35 cycles of either pembrolizumab or ramucirumab will discontinue study treatment but will continue to be followed for survival and toxicity unless the patient withdraws consent. Likewise, patients who are removed for other reasons listed above may still be followed for survival and toxicity unless study consent is withdrawn.

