6.1 Study Assessments

6.1.1 Efficacy Assessments

Primary Endpoint: The response rate of R+P will be evaluated using RECIST 1.1 as well as iRECIST. Disease status will be measured by CT scan at baseline and then once every two cycles and as clinically indicated. Radiographic response per RECIST v.1.1 and iRECIST criteria (Appendices 1 and 2) will be determined by comparison to the tumor measurement obtained at baseline. Tumor progression will be determined by comparison to the smallest tumor measurement at either baseline or after initiation of therapy. The baseline disease assessment must be recorded and measured within 28 days prior to treatment start. During the treatment period, disease assessments will be performed every 6 weeks, i.e. once every two cycles, and as clinically indicated.

Secondary Endpoints: Safety and tolerability will be assessed with adverse event (AE) assessments at each study visit. CTCAE v5.0 will be used for adverse event grading. Attributions of causality will be assessed by the primary treating physician. Clinical benefit rate (stable disease + responses) will be assessed using the same criteria as response rate and on the same schedule. Survival will be measured from the date of study registration to the date of event (i.e., death or progressive disease) or the date of last follow-up if no event has occurred at their last evaluation.

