6.3.6 End of Treatment and Follow-up Tumor Imaging

Patients who discontinue therapy for any reason must have an end of treatment (EOT) visit completed 30 days (\pm 14 days) after the last application of study drug.

At the EOT visit, the patients will undergo the following assessments:

Physical examination and vital signs	
• Body weight• Blood pressure, pulse, temperature• Physical examination
Urine analysis	Urine bilirubin, glucose, hemoglobin, ketones, pH, protein
Hematology	Hemoglobin, hematocrit, mean corpuscular volume, mean corpuscular hemoglobin, mean corpuscular hemoglobin concentration, white blood cell (WBC) count, WBC differential, red blood cell count, lymphocytes, monocytes, neutrophils, band neutrophils, eosinophils, basophils, platelets. WBC differential may be automated or manual as per institutional standards.
Complete serum chemistry	Sodium, potassium, chloride, bicarbonate, BUN, creatinine, glucose, calcium, phosphate, magnesium, ALT, AST, alkaline phosphatase, total bilirubin, total protein, albumin
Assessment of disease status	CT scan (if not performed within the last 28 days)
Adverse events and concomitant medication	Assessed on an ongoing basis

PROTOCOL NUMBER: OSU-19132

In participants who discontinue study treatment, tumor imaging should be performed at the time of treatment discontinuation (± 4 week window). If previous imaging was obtained within 4 weeks prior to the date of discontinuation, then imaging at treatment discontinuation is not mandatory. In participants who discontinue study treatment due to documented disease progression and the Investigator elects not to implement iRECIST, this is the final required tumor imaging.

In participants who discontinue study treatment without documented disease progression, every effort should be made to continue monitoring their disease status by tumor imaging using the same imaging schedule used while on treatment (every 12 weeks in Year 1 or every 24 weeks after Year 1) to monitor disease status until the start of a new anticancer treatment, disease progression, pregnancy, death, withdrawal of consent, or the end of the study, whichever occurs first.

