6.3.7 Post-treatment follow-up

Patient status will continue to be evaluated post-study. Patients will be contacted via telephone every 3 months for the first year after study completion. Beyond 1 year post-treatment, patients will be contacted every 6 months to obtain information for post-study survival data. Patients will be asked to supply the name and addresses of two contact people who the site may contact to assist with phone follow-up. Post-study survival data may alternatively be obtained during patient visits to site or source documents from other medical visits.

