6.5 Planned Treatment of the Patients after End of Treatment Phase

After completion of the study at routine follow-up (EOT), patients will generally be treated at the discretion of the investigator according to medical routine.

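### PFS is censored at last contact or last follow-up, not at the last tumor assessment, so unscanned time can count as progression-free

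*Combined protocol and SAP*

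**What the plan says.** Section 9.4.2, repeated word for word in the synopsis, states: "Patients who have reached the end of the study but not progressed will be considered censored at the last documented date of contact". Since it turns on not having progressed, it is a rule for PFS.

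Section 6.1.1 measures survival from registration and gives the event and the censoring date as "death or progressive disease) or the date of last follow-up if no event has occurred at their last evaluation". The last-follow-up sentence in 9.4.1 is written for OS, where it is appropriate.

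Other sections decide how long patients are scanned and how long they are contacted:

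- Section 6.3.6: "tumor imaging should be performed at the time of treatment discontinuation", with a 4-week window. Patients who stop without progression continue imaging "until the start of a new anticancer treatment, disease progression, pregnancy, death, withdrawal of consent, or the end of the study, whichever occurs first".
- Section 4.5: "patients who are removed for other reasons listed above may still be followed for survival and toxicity unless study consent is withdrawn".
- Section 6.3.7: patients are "contacted via telephone every 3 months for the first year after study completion", then every 6 months, for survival data.
- Section 6.5 opens: "After completion of the study at routine follow-up (EOT), patients will generally be treated".

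No section sets the PFS censoring date at the last tumor assessment, and none says how PFS treats the start of new anticancer therapy.

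**The concern.** Progression is found by imaging. A patient who stops study treatment without progression and starts another therapy has no further planned scans but can still be reached for survival. Read literally, the rule keeps that patient in the PFS risk set until the last contact, although progression can no longer be observed.

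Such patients are foreseeable: 9.4.2 itself plans to report how many go off treatment for adverse reactions or refuse further treatment. At stake are the Kaplan-Meier PFS estimates, which 9.4.2 intends as preliminary data for later research and which would lean upward.

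**Working it through.** The documents state no planning figure for PFS, so there is none to reproduce. The direction follows from the formula; the size needs assumptions.

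**1. Direction.** The estimate is S(t) = product over event times t_j ≤ t of (1 − d_j/n_j), where d_j is the number of events at t_j and n_j the number still at risk. Hold the events fixed and move a censoring date later. No n_j falls, so no factor 1 − d_j/n_j falls, and S(t) stays equal or rises. This needs no assumption about the trial.

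**2. Does contact outlast imaging?** New therapy ends imaging (6.3.6). Survival follow-up may continue (4.5), by telephone or other sources (6.3.7). Whether those calls are contact for PFS is not settled:

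- Section 6.3.7 places the calls after study completion, and 6.5 ties completion to the end-of-treatment (EOT) visit. This supports contact ending at EOT, about 30 days after the last dose.
- Section 6.3.6 lets off-treatment imaging run up to the end of the study. That cannot mean EOT there, or there would be almost no such imaging.

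**3. Size, by large-sample simulation.**

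- *From the documents:* scans every 6 weeks for 6 months, then every 12 weeks (6.3.5); a CT at discontinuation unless one was done within 4 weeks (6.3.6); calls every 3 months for a year, then every 6 months (6.3.7); 34 patients; a 9.7-month median PFS from the phase 1 cohort (1.5.2), as the upper case.
- *Assumed:* exponential PFS with median 3, 4, 6 or 9.7 months; 20% leaving without progression in months 1-4, independently of progression; post-progression survival median 10 months; scans continuing on the same schedule until new therapy, which starts at once or 3 months after stopping; cutoff at 24 months.
- *Events:* progression dated at the detecting scan, and all deaths, as in 6.1.1, under both rules. Only the censoring date differs.

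Excess of last-contact over last-assessment PFS, in percentage points, across the four medians:

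| Situation | 6 months | 12 months |
|---|---|---|
| Calls count, new therapy at once | 2.0 to 2.2 | 3.1 to 4.4 |
| Calls count, new therapy 3 months later | 0.4 to 0.5 | 1.8 to 3.1 |
| No leavers | about 0 | about 0 |

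For example, with median 4 months and new therapy at once, 6-month PFS is 43.4% under last contact and 41.3% under last assessment: 43.4 − 41.3 = 2.1 points.

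If contact ends at EOT, the 6-month excess is about 0 to 1.6 points. That is an upper figure, because the comparison also leaves out deaths after new therapy.

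**4. Median.** Changing only the censoring date left the Kaplan-Meier median unchanged in 7 of 8 cells (four medians, two delays), because it tends to fall on a scan date. The exception was a true median of 9.7 months with new therapy at once, where it moved from 11.0 to about 13 months.

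**5. Scale.** Ignoring censoring, the standard error of a 43.4% estimate from 34 patients is √(0.434 × 0.566 / 34) = 0.085, or 8.5 points; simulated trials of 34 gave 7.6 to 9.4. The 2.1-point shift is about 2.1/8.5 = 0.25 of a standard error.

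**The case against.** The strongest reply is that the rule applies to patients who have reached the end of the study, that 6.3.7 and 6.5 put the telephone calls after that point, and that a CT is due around discontinuation. Contact and last scan would then lie close together and the effect would be small. This is a fair reading. If leaving is also related to prognosis, the sign of the error against uninterrupted scanning is not even fixed on this reading (−2.0 to +7.4 points at 6 months under the patterns tried). It does not settle the matter, because 6.3.6 uses the end of the study in a wider sense.

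Second, 6.1.1 refers to the last evaluation, which may suggest a scan. But that phrase conditions event-free status; the date named is still last follow-up.

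Third, the synopsis and 7.3 let one drug continue when the other stops for toxicity, which limits the number of leavers. That stands: their share is unknown, and with none the two rules agree.

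Fourth, the shift is well inside sampling error, PFS carries no test or decision, and last-assessment censoring can itself be informative. All of this stands and lowers the severity. It does not justify the rule: a confidence interval shows sampling error but not a shift from the choice of censoring date.

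**Conclusion.** The point holds at low severity. The plan states a PFS censoring date that is not tied to tumor assessment, and with the same events counted that choice can only leave Kaplan-Meier PFS equal or higher. Under the assumptions above the date alone is worth about 2 points at 6 months and 3-4 at 12 months with immediate new therapy, about 0.5 and 2-3 with a 3-month delay, about 0-1.6 at 6 months if contact ends at EOT, and about zero without leavers. The share leaving, the delay to new therapy, post-progression survival and independent leaving are all assumed, so the true size is not derivable from the documents.

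A reader might infer a larger error by comparing 43.4% with 37.7% at 6 months (median 4, new therapy at once), a gap of 5.7 points. The documents do not support reading that as the effect of the censoring date. The 37.7% also drops deaths after new therapy, whereas 6.1.1 counts death without exception. With all deaths kept, the figure is 41.3%: 2.1 points come from the date and 41.3 − 37.7 = 3.6 from which deaths count, and the latter is a trade-off rather than an error. Nor do the documents support saying that median PFS will generally be inflated, that the calls certainly count as contact, or that the ORR decision rule is affected.

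**What to change.** In 9.4.2, 6.1.1 and the synopsis, state that patients without a PFS event are censored at their last evaluable tumor assessment showing no progression. Keep last-contact censoring for OS only, and keep death or progressive disease as the PFS event. Record the start date of new anticancer therapy, and show alternative handling of new therapy as a sensitivity analysis.

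The sensitivity analysis matters because the conventions differ. With median 4 and new therapy at once, 6-month PFS under last-assessment censoring is 41.3% with all deaths counted and 37.7% without deaths after new therapy; it is 30.7% if new therapy is itself an event.

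The cost is one sentence in three places, one recorded date (which 6.3.6 already needs, since it ends imaging) and a short additional analysis. Reported PFS may be slightly lower. Censoring at the last assessment may also be informative: under two assumed patterns of prognosis-related leaving, with deaths after new therapy not counted, it was itself off by −3.9 to +6.2 points at 6 months against uninterrupted scanning. The report should state that limitation.

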	
Tumor type: EGFR mutation positive NSCLC
 
The proposed study will be an open-label single arm phase II trial of ramucirumab and pembrolizumab (R+P) in EGFR mutant NSCLC after progression on tyrosine kinase inhibitors (TKIs). Patients are required to receive at least one TKI (erlotinib, gefitinib, afatinib or osimertinib). Post-TKI chemotherapy is also permitted.
 
Each treatment cycle will be 21 days; patients will receive ramucirumab 10 mg/kg IV and pembrolizumab 200 mg IV and on day 1. Dosing of ramucirumab and pembrolizumab is based on prior phase 1 testing of the combination. A two-stage design will be utilized to minimize exposure to combination therapy if there is limited efficacy. The initial stage will enroll 13 patients; if ≥ 1 patient has a confirmed response, the study will continue and enroll an additional 21 patients for a total of 34 patients.
 
Response will be assessed using RECIST (RECIST 1.1 and iRECIST). Imaging will be performed every 6 weeks/2 cycles to assess response. Patients with clinical benefit may continue therapy beyond progression for up to 2 cycles – if progressive disease confirmed on repeat imaging, therapy would be discontinued. Toxicity will be assessed using CTCAE v5.0. Progression free survival will be assessed using RECIST and will be assessed starting from date of study enrollment.
 
Blood samples tissue will be collected at baseline (day 1, cycle 1), cycle 3 day1 (approx. 6 weeks), and at study discontinuation (or progression). Archival tissue will be requested at enrollment for correlative studies.

Duration of Treatment	Patients may continue to receive study treatment (R+P) until radiographic documentation of disease progression, the occurrence of unacceptable toxicity or of the occurrence of other withdrawal criteria. If either drug is discontinued due to toxicity, the other drug may be continued.
Inclusion /Exclusion Criteria	
Inclusion Criteria:
 
1. Adult patients aged ≥ 18 years

IRB Protocol Number: 2019C0145
IRB Approval date: 06/10/2022
Version: 05/06/2022

PROTOCOL NUMBER: OSU-19132

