3.2 Study Duration

Patients will receive pembrolizumab and ramucirumab day 1 during each 21-day cycle. Patient may continue on study drugs until disease progression or for up to 35 cycles. Objective assessment of disease progression will be performed every six weeks.

IRB Protocol Number: 2019C0145
IRB Approval date: 06/10/2022
Version: 05/06/2022

PROTOCOL NUMBER: OSU-19132

[figure not shown]
The study enrolled first patient in Summer 2020 with respect to first patient in (FPI). With an expected accrual rate of 1 patients every 2months, and a total number of 34 patients planned (if trial proceeds to second stage), the anticipated enrollment period is 60 months with the last patient enrolled by Summer2025. The anticipated length of treatment period will be approximately 3-6 months, leading to the last patient off study treatment in November-December 2025. The primary endpoint analysis will be done after the last accrued patient has been followed for at least 6 weeks.

IRB Protocol Number: 2019C0145
IRB Approval date: 06/10/2022
Version: 05/06/2022

PROTOCOL NUMBER: OSU-19132

[figure not shown]

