4.1 Study Population and Sample Size

This trial will be open to non-small cell lung cancer (NSCLC) patients with sensitizing EGFR mutations who have received first or second line therapy with tyrosine kinase inhibitor (TKI). These are most commonly lung adenocarcinoma but there are no restrictions for histology.

Planned enrollment is up to 34 patients. There will be a 2 stage design with a planned interim analysis for futility planned after the initial 13 patients (stage 1) have been followed for at least 6 weeks.

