6.3.5 Tumor Imaging on Study

The first on-study imaging assessment should be performed at 6 weeks (42 days \pm 7 days) from the date of allocation. Subsequent tumor imaging should be performed every 6 weeks (42 days \pm 7 days) or more frequently if clinically indicated. After 6 months, participants who remain on treatment will have imaging performed every 12 weeks (84 days \pm 7 days). Imaging timing should follow calendar days and should not be adjusted for delays in cycle starts. Imaging should continue to be performed until disease progression is identified by the Investigator.

Objective response should be confirmed by a repeat imaging assessment. Tumor imaging to confirm PR or CR should be performed at least 4 weeks after the first indication of a response is observed. Participants will then return to regular scheduled imaging every 6 weeks, starting with the next scheduled imaging time point. Participants who receive additional imaging for confirmation do not need to undergo the next scheduled tumor imaging if it is less than 4 weeks later; tumor imaging may resume at the subsequent scheduled imaging time point.

PROTOCOL NUMBER: OSU-19132

Per iRECIST (Appendix 2), disease progression should be confirmed by the site 4 to 8 weeks after first radiologic evidence of PD in clinically stable participants as defined by Appendix 2 (Note- if patient is receiving clinical benefit, oligoprogressive CNS disease that can be controlled with local therapy such as stereotactic radiation, may continue on treatment beyond progression with PI approval. Ramucirumab should be held for 2 weeks prior to radiation. Patient can have radiation for CNS oligoprogression as long as ramucirumab is held for 4-6 weeks afterwards. Ramucirumab can be restarted after this time if the patient is asymptomatic, clinically stable and this is considered appropriate by the investigator.). Participants who have unconfirmed disease progression may continue on treatment at the discretion of the Investigator until progression is confirmed by the site provided they have met the conditions detailed in Section 9.2.1.6. Participants who receive confirmatory imaging do not need to undergo the next scheduled tumor imaging if it is less than 4 weeks later; tumor imaging may resume at the subsequent scheduled imaging time point, if clinically stable. Participants who have confirmed disease progression by iRECIST, as assessed by the site, will discontinue study treatment.

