6.4 End of Study

The primary statistical analysis will be performed when 80% of the events for the secondary analysis of PFS have occurred. This will ensure appropriate follow-up time for the primary endpoint of ORR and for the secondary endpoints of PFS and OS.

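### The plan does not say consistently whether a response must be confirmed to count against the two Simon cutoffs, and it allows the stage 1 look before a late responder can be confirmed

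*Combined protocol and SAP*

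**What the plan says.** **Where confirmation appears.** The study design part of the synopsis continues to stage 2 if at least one "patient has a confirmed response, the study will continue". Section 6.3.5 says an objective response should be confirmed by repeat imaging: "Tumor imaging to confirm PR or CR should be performed at least 4 weeks after the first indication of a response is observed".

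**Where it does not.** Section 9.4.2 takes best response in evaluable patients: "Those who achieve a partial response (PR) or complete response (CR) will be considered responses". Appendix 1 defines CR and PR without confirmation. Sections 9.2, 9.3 and 9.4.1, and the statistical part of the synopsis, speak only of responses or of patients responding.

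**Timing.** Under 6.3.5 the first on-study scan is at 42 ± 7 days, and "Subsequent tumor imaging should be performed every 6 weeks" for the first 6 months. Section 4.1 has a "planned interim analysis for futility planned after the initial 13 patients (stage 1) have been followed for at least 6 weeks". For the final look, section 3.2 says: "The primary endpoint analysis will be done after the last accrued patient has been followed for at least 6 weeks". Section 6.4 gives a different trigger: "The primary statistical analysis will be performed when 80% of the events for the secondary analysis of PFS have occurred".

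**Stage 1 cutoff.** Both synopsis statements and 9.3 stop at 0 of 13. Sections 9.2 and 9.4.1 stop at 1 or fewer of 13. Section 9.4.1 then rejects the combination at 5 or fewer of 34.

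**The concern.** Both decisions compare a very small count with a fixed cutoff, so one patient can change the result. If the plan does not fix whether a PR seen on a single scan counts, two analysts following it could reach different go/no-go decisions from the same scans, and the choice could be made after the data are known.

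Timing adds to this. If the stage 1 count is of confirmed responses but the look takes place at the 6-week minimum, a genuine responder enrolled last cannot yet qualify. The two stage 1 cutoffs matter here because the cost of losing one responder depends on which applies.

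**Working it through.** **1. Reproduce the stated design.** Inputs from 9.4.1: 13 patients then 21, null rate 0.10, alternative 0.25, final rejection at 5 or fewer of 34. With r1 the stage 1 stopping count:

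- PET = P(X1 ≤ r1), with X1 ~ Bin(13, p)
- E[N] = 13 + (1 − PET) × 21
- P(pass) = sum over x > r1 of P(X1 = x) × P(X2 ≥ 6 − x), with X2 ~ Bin(21, p)

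For r1 = 1 at p = 0.10: PET = 0.9^13 + 13 × 0.1 × 0.9^12 = 0.2542 + 0.3672 = 0.621, and E[N] = 13 + 0.3787 × 21 = 20.95. Both match 9.4.1. For r1 = 0: PET = 0.9^13 = 0.254, and E[N] = 13 + 0.7458 × 21 = 28.7.

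| Stage 1 stop | Stated in | PET at 10% | E[N] at 10% | Alpha | Power at 25% |
|---|---|---|---|---|---|
| 1 or fewer of 13 | 9.2, 9.4.1 | 0.621 | 20.95 | 0.096 | 0.811 |
| 0 of 13 | synopsis, 9.3 | 0.254 | 28.7 | 0.115 | 0.876 |

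The stated properties belong only to the first row. The second row exceeds the planned alpha of 0.10.

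**2. When can a response be confirmed?** Follow-up is counted from the date that starts the imaging calendar.

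- First scan: day 42 ± 7, so day 35 to 49.
- Extra scan at least 28 days later: day 63 (35 + 28) to day 77 (49 + 28) at the earliest.
- Second regular scan: 84 ± 7, so day 77 to 91.

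A patient with 42 days of follow-up therefore cannot have a confirmed response on the planned schedule.

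**3. How many patients does this affect?** Section 3.2 plans "With an expected accrual rate of 1 patients every 2months", about 61 days apart. When patient 13 reaches day 42, patient 12 is at about day 42 + 61 = 103, past day 91. At that pace usually only patient 13 is affected.

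**4. Effect at stage 1, true rate 25%.** Score patient 13 as a non-responder at the look, so that 12 patients can contribute, but count all 34 at the end.

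- Stop at 0: 0.75^13 = 2.4% becomes 0.75^12 = 3.2%. Power goes from 0.876 to 0.871.
- Stop at 1 or fewer: 0.0238 + 13 × 0.25 × 0.75^12 = 12.7% becomes 0.0317 + 12 × 0.25 × 0.75^11 = 15.8%. Power goes from 0.811 to 0.785.

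The second line combines the synopsis's confirmation condition with the cutoff in 9.2 and 9.4.1, which does not mention confirmation.

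**5. If the count and the planning rates differ in definition.** The documents do not say whether 10% and 25% are confirmed rates, nor what fraction of responses confirm. As an assumption only, take fractions of 90% and 80% on both sides, under the 9.4.1 rule:

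| Fraction confirming | 10% is confirmed, unconfirmed responses counted | 25% is unconfirmed, confirmed responses counted |
|---|---|---|
| 90% | rate 0.10/0.9 = 0.111, alpha 0.139 | rate 0.25 × 0.9 = 0.225, power 0.725 |
| 80% | rate 0.10/0.8 = 0.125, alpha 0.203 | rate 0.25 × 0.8 = 0.200, power 0.614 |

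If the definitions match, alpha 0.096 and power 0.811 stand.

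**The case against.** The best defence is that the plan, read as a whole, already points to confirmed response. Section 6.3.5 sets a study-wide imaging rule, 1.5.4 makes RECIST 1.1 the primary measure, and silence in 9.4.2 is not contradiction. This has force and supports the fix below. It does not remove the gap: 6.3.5 is worded as a recommendation, and the only formula for the primary endpoint omits the condition.

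A reader might go further and infer several things that the documents do not support:

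- **That confirmation is mandatory throughout.** Only the synopsis gate makes it a condition.
- **That the look must take place at 6 weeks.** Six weeks is a minimum. A team may wait for a pending confirmation, and 6.3.5 allows extra scans when clinically indicated.
- **That the timing alone does serious damage.** The one gate that says confirmed uses the 0-of-13 cutoff, where the effect is under one percentage point. The larger figure needs confirmation to be carried over to a cutoff that does not mention it.
- **That the error rates are wrong.** The alpha and power shifts in step 5 rest on confirmation fractions found nowhere in the plan.
- **That the final look has the same fault.** This is so only under the 6-week minimum in 3.2. Section 6.4 sets a different trigger, expressly to give adequate follow-up for response rate.

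**Conclusion.** The point holds as an inconsistency in the primary count and its stage 1 cutoff that should be corrected. It is not an error in the published design calculation, which reproduces exactly for the 1-or-fewer rule.

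The cutoff conflict needs no assumption about confirmation: early termination under the null is 0.254 or 0.621, and alpha 0.115 or 0.096, depending on the section followed. The timing effect is small under the synopsis cutoff and moderate under 9.4.1, where power would fall just below the planned 80%. Both timing figures assume a look at the earliest permitted time, accrual as planned, and a pending response scored as none. The size of any mismatch between the count and the planning rates cannot be determined from the documents.

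**What to change.** - In 9.1.1, 9.4.1 and 9.4.2, use one numerator for both cutoffs: confirmed CR or PR by RECIST 1.1. This fits the synopsis gate, 1.5.4 and 6.3.5.
- State that 10% and 25% are on that basis. If they are not, recheck alpha and power.
- Reconcile the stage 1 cutoff across the synopsis, 9.2, 9.3 and 9.4.1, and state the operating characteristics that go with it.
- Do not declare a stage 1 stop while any of the 13 has an unconfirmed CR or PR awaiting its confirmatory scan, whichever scan first showed it. Set the minimum follow-up in 4.1 to cover the first scan plus confirmation, about 11 to 13 weeks (day 77 to 91).
- Reconcile 3.2 with 6.4 so that the final look meets the same condition.
- Report unconfirmed and iRECIST response rates as sensitivity analyses.

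**Cost.** A few sentences; the scans are already provided for. The stage 1 look may wait up to 91 − 42 = 49 days (7 weeks) longer, which is less than one patient of accrual at the planned rate. The wait is longer if a response first appears at the second scan: that scan falls at day 77 to 91, so confirmation comes at day 105 to 119 at the earliest. The reported response rate may be slightly lower.
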